5.6 Rescue Medications & Supportive Care

5.6.1 Supportive Care Guidelines

Adverse events experienced on study may be related to the study agent (pembrolizumab), enzalutamide, cancer itself, or another etiology. If the side effect is felt related to the pembrolizumab, please follow the recommended supportive care guidelines below. If the side effect is attributable to something other than pembrolizumab, these guidelines may not apply, and a more appropriate treatment may be needed. Subjects should receive appropriate supportive care measures as deemed necessary by the treating investigator including but not limited to the items outlined below:

- Diarrhea: Subjects should be carefully monitored for signs and symptoms of enterocolitis (such as diarrhea, abdominal pain, blood or mucus in stool, with or without fever) and of bowel perforation (such as peritoneal signs and ileus). In symptomatic subjects, infectious etiologies should be ruled out, and if symptoms are persistent and/or severe, endoscopic evaluation should be considered.
 - In subjects with severe enterocolitis (Grade >2), pembrolizumab will be permanently discontinued and treatment with systemic corticosteroids should be initiated at a dose of 1 to 2 mg/kg/day of prednisone or equivalent. When symptoms improve to Grade 1 or less, corticosteroid taper should be started and continued over at least 1 month.
 - In subjects with moderate enterocolitis (Grade 2), pembrolizumab should be withheld and anti-diarrheal treatment should be started. If symptoms are persistent for more than one week, systemic corticosteroids should be initiated (e.g., 0.5 mg/kg/day of prednisone or equivalent). When symptoms improve to Grade 1 or less, corticosteroid taper should be started and continued over at least 1 month. Regarding guidelines for continuing treatment with pembrolizumab, see Section 5.2.
 - All subjects who experience diarrhea should be advised to drink liberal quantities of clear fluids. If sufficient oral fluid intake is not feasible, fluid and electrolytes should be substituted via IV infusion.

- Nausea/vomiting: Nausea and vomiting should be treated aggressively, and consideration should be given in subsequent cycles to the administration of prophylactic antiemetic therapy according to standard institutional practice. Subjects should be strongly encouraged to maintain liberal oral fluid intake.
- Anti-infectives: Subjects with a documented infectious complication should receive oral or IV antibiotics or other anti-infective agents as considered appropriate by the treating investigator for a given infectious condition, according to standard institutional practice.
- Immune-related adverse events: Please see Section 5.6.1.1 below and Section 12.6 regarding diagnosis and management of adverse experiences of a potential immunologic etiology.
- Management of Infusion Reactions: Acute infusion reactions (which can include cytokine release syndrome, angioedema, or anaphylaxis) are different from allergic/hypersensitive reactions, although some of the manifestations are common to both AEs. Signs and symptoms usually develop during or shortly after drug infusion and generally resolve completely within 24 hours of completion of infusion. Signs/symptoms may include: Allergic reaction/hypersensitivity (including drug fever); Arthralgia (joint pain); Bronchospasm; Cough; Dizziness; Dyspnea (shortness of breath); Fatigue (asthenia, lethargy, malaise); Headache; Hypertension; Hypotension; Myalgia (muscle pain); Nausea; Pruritis/itching; Rash/desquamation; Rigors/chills; Sweating (diaphoresis); Tachycardia; Tumor pain (onset or exacerbation of tumor pain due to treatment); Urticaria (hives, welts, wheals); Vomiting.

Table 4 below shows treatment guidelines for subjects who experience an infusion reaction associated with administration of pembrolizumab.

Table 4 Infusion Reaction Treatment Guidelines

NCI CTCAE Grade	Treatment	Premedication at subsequent dosing
Grade 1 Mild reaction; infusion interruption not indicated; intervention not indicated	Increase monitoring of vital signs as medically indicated until the subject is deemed medically stable in the opinion of the investigator.	None
Grade 2 Requires infusion interruption but responds promptly to symptomatic treatment (e.g., antihistamines, NSAIDS, narcotics, IV fluids); prophylactic medications indicated for <=24 hrs	Stop Infusion and monitor symptoms. Additional appropriate medical therapy may include but is not limited to: IV fluids Antihistamines NSAIDS Acetaminophen Narcotics Increase monitoring of vital signs as medically indicated until the subject is	Subject may be premedicated 1.5h (\pm 30 minutes) prior to infusion of pembrolizumab with: Diphenhydramine 50 mg po (or equivalent dose of antihistamine).

NCI CTCAE Grade	Treatment	Premedication at subsequent dosing
	
deemed medically stable in the opinion of the investigator.
 
If symptoms resolve within one hour of stopping drug infusion, the infusion may be restarted at 50% of the original infusion rate (e.g. from 100 mL/hr to 50 mL/hr).
 
Otherwise dosing will be held until symptoms resolve and the subject should be premedicated for the next scheduled dose.
 
Subjects who develop Grade 2 toxicity despite adequate premedication should be permanently discontinued from further trial treatment administration.
	Acetaminophen 500-1000 mg po (or equivalent dose of antipyretic).
Grades 3 or 4 Grade 3: Prolonged (i.e., not rapidly responsive to symptomatic medication and/or brief interruption of infusion); recurrence of symptoms following initial improvement; hospitalization indicated for other clinical sequelae (e.g., renal impairment, pulmonary infiltrates) Grade 4: Life-threatening; pressor or ventilatory support indicated	
Stop Infusion.
 
Additional appropriate medical therapy may include but is not limited to:
 
IV fluids Antihistamines NSAIDS Acetaminophen Narcotics Oxygen Pressors Corticosteroids Epinephrine
 
Increase monitoring of vital signs as medically indicated until the subject is deemed medically stable in the opinion of the investigator.
 
Hospitalization may be indicated.
 
Subject is permanently discontinued from further trial treatment administration.
	No subsequent dosing

Appropriate resuscitation equipment should be available in the room and a physician readily available during the period of drug administration.
 
For Further information, please refer to the Common Terminology Criteria for Adverse Events v4.0 (CTCAE) at http://ctep.cancer.gov
		

5.6.1.1 Supportive Care Guidelines for Immune-related Adverse Events (irAEs)

Events of clinical interest of a potential immunologic etiology (irECIs) may be defined as an adverse event of unknown etiology, associated with drug exposure and is consistent with an immune phenomenon. irAEs may be predicted based on the nature of the pembrolizumab compound, its mechanism of action, and reported experience with immunotherapies that have a similar mechanism of action. Special attention should be paid to AEs that may be suggestive of potential irAEs. An irAE can occur shortly after the first dose or several months after the last dose of treatment.

If an irAE is suspected, efforts should be made to rule out neoplastic, infectious, metabolic, toxin or other etiologic causes prior to labeling an adverse event as an irAE. Information on how to

identify and evaluate irAEs has been developed and is included in the Event of Clinical Interest and Immune-Related Adverse Event Guidance Document. See Section 12.6. Subjects who develop a Grade 2 or higher irAE should be discussed immediately with the Sponsor.

Recommendations to managing irAEs not detailed elsewhere in the protocol are detailed in Table 5.

Table 5 General Approach to Handling irAEs

irAE	Withhold/Discontinue Pembrolizumab?	Supportive Care
Grade 1	No action	Provide symptomatic treatment
Grade 2	May withhold pembrolizumab	Consider systemic corticosteroids in addition to appropriate symptomatic treatment
Grade 3 and Grade 4	Withhold pembrolizumab Discontinue if unable to reduce corticosteroid dose to < 10 mg per day prednisone equivalent within 12 weeks of toxicity	Systemic corticosteroids are indicated in addition to appropriate symptomatic treatment. May utilize 1 to 2 mg/kg prednisone or equivalent per day. Steroid taper should be considered once symptoms improve to Grade 1 or less and tapered over at least 4 weeks.

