5.2.1.2 Dose Modification

Pembrolizumab will be withheld for drug-related Grade 4 hematologic toxicities, non-hematological toxicity \geq Grade 3 including laboratory abnormalities, and severe or life-threatening AEs as per Table 3 below.

Table 3: Dose modification guidelines for non-immune related drug-related adverse events.

Toxicity	Grade	Hold Treatment (Y/N)	Timing for restarting treatment	Dose/Schedule for restarting treatment	Discontinue Subject (after consultation with Coordinating Center, OHSU)
Hematological Toxicity	1, 2	No	N/A	N/A	N/A
	3* *Excluding Grade 3 neutropenia, anemia, and thrombocytopenia	Yes	Toxicity resolves to Grade 0-1 or baseline	May increase the dosing interval by 1 week	Toxicity does not resolve within 12 weeks of last infusion
	4	Yes	Toxicity resolves to Grade 0-1 or baseline	May increase the dosing interval by 1 week	Permanent discontinuation should be considered for any severe or life-threatening event
Non-hematological toxicity Note: Exception to be treated similar to grade 1 toxicity • Grade 2 alopecia • Grade 2 fatigue For additional information regarding Adverse Events with	1	No	N/A	N/A	N/A
	2	Consider withholding for persistent symptoms	Toxicity resolves to Grade 0-1 or baseline	Clinical AE resolves within 4 weeks: Same dose and schedule (reference Section 5.6.1.2 for recommendations regarding pneumonitis)	Toxicity does not resolve within 12 weeks of last infusion

Toxicity	Grade	Hold Treatment (Y/N)	Timing for restarting treatment	Dose/Schedule for restarting treatment	Discontinue Subject (after consultation with Coordinating Center, OHSU)
a potential Immune-Etiology reference Section 5.6.1.1.				Clinical AE does not resolve within 4 weeks: May increase the dosing interval by 1 week for each occurrence	
	3, 4	Yes	Toxicity resolves to Grade 0-1 or baseline	May increase the dosing interval by 1 week for each occurrence	Toxicity does not resolve within 12 weeks of last infusion Permanent discontinuation should be considered for any severe or life-threatening event

In case toxicity does not resolve to Grade 0-1 within 12 weeks after last infusion, trial treatment should be discontinued after consultation with [name] at OHSU. With investigator and [name] agreement, subjects with a laboratory adverse event still at Grade 2 after 12 weeks may continue treatment in the trial only if asymptomatic and controlled. For information on the management of adverse events, see Section 5.6.1.

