7.2.3.2 Events of Clinical Interest

Selected non-serious and serious adverse events are also known as Events of Clinical Interest (ECI) and must be recorded as such on the Adverse Event case report forms/worksheets and reported within 24 hours to the Sponsor and within 2 working days to Merck Global Safety. (Attn: Worldwide Product Safety; [contact])

Events of clinical interest for this trial include:

1. an overdose of Merck product, as defined in Section 7.2.1 - Definition of an Overdose for This Protocol and Reporting of Overdose to the Sponsor, that is not associated with clinical symptoms or abnormal laboratory results.
2. an elevated AST or ALT lab value that is greater than or equal to 3X the upper limit of normal and an elevated total bilirubin lab value that is greater than or equal to 2X the upper limit of normal and, at the same time, an alkaline phosphatase lab value that is less than 2X the upper limit of normal, as determined by way of protocol-specified laboratory testing or unscheduled laboratory testing.*

***Note:** These criteria are based upon available regulatory guidance documents. The purpose of the criteria is to specify a threshold of abnormal hepatic tests that may require an additional evaluation for an underlying etiology. The trial site guidance for assessment and follow up of these criteria can be found in the Investigator Trial File Binder (or equivalent).

3. In the event a subject develops any of the following AEs, a detailed narrative of the event should be reported as an ECI to the Sponsor within 24 hours and to Merck Global Safety within 2 working days of the event:
 - a. Grade ≥ 3 diarrhea
 - b. Grade ≥ 2 colitis
 - c. Grade ≥ 2 pneumonitis
 - d. Grade ≥ 3 hypo- or hyperthyroidism

A separate guidance document has been provided entitled “event of Clinical Interest and Immune-Related Adverse Event Guidance Document.” This document provides guidance regarding identification, evaluation and management of ECIs and irAEs. Additional ECIs are identified in this guidance document and also need to be reported to the Sponsor within 24 hours and to Merck Global Safety within 2 working days of the event.

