Each of the events above is described within this guidance document, along with site requirements for reporting these events to the Sponsor. The information collected should be entered into the narrative field(s) of the Adverse Event module in the database (please note, if narrative entry into the database is not available, please use the narrative text box on the 1727/AER Form). If additional Medical History or Concomitant Medications are reported, the Medical History and Concomitant Medication modules in the database must be updated.

In addition, the guidelines include recommendations on the management of these ECIs. These guidelines are intended to be applied when the physician determines the events to be related to pembrolizumab. Note: if after the evaluation the event is determined not to be related, the physician is instructed to follow the ECI reporting guidance but does not need to follow the treatment guidance (below). Therefore, these recommendations should be seen as guidelines and the treating physician should exercise individual clinical judgment based on the patient. For any question of dose modification or other treatment options, the specific language in the protocol should be followed. Any questions pertaining to the collection of this information or management of ECIs should be directed to your local Sponsor contact.

Dose Modification/Discontinuation

The treatment guidance provides specific direction when to hold and/or discontinue pembrolizumab for each immune related adverse event. Of note, when the guidance states to “discontinue” pembrolizumab this is the permanent discontinuation of treatment with pembrolizumab. “Hold” means to stop treating with pembrolizumab but resumption of treatment may be considered assuming the patient meets the criteria for resumption of treatment.

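### Table 5 leaves a restart open after Grade 3-4 immune events that Section 12.6 stops permanently; 12.6 probably governs, but the protocol does not shut out the other reading

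*Combined protocol and SAP*

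**What the plan says.** Section 5.6.1.1, Table 5, Grade 3 and Grade 4 row: "Withhold pembrolizumab Discontinue if unable to reduce corticosteroid dose to < 10 mg per day prednisone equivalent within 12 weeks of toxicity". The sentence introducing the table limits its reach: "Recommendations to managing irAEs not detailed elsewhere in the protocol are detailed in Table 5".

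The guidance document reproduced as Section 12.6 separates a hold, after which treatment may resume, from discontinuation, of which it says "this is the permanent discontinuation of treatment with pembrolizumab". It then gives instructions by event type and grade. Its Overview also says that "these recommendations should be seen as guidelines and the treating physician should exercise individual clinical judgment based on the patient", and adds: "For any question of dose modification or other treatment options, the specific language in the protocol should be followed".

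Three cross-references connect the texts:

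- Section 5.6.1 cites both without ranking them: "Please see Section 5.6.1.1 below and Section 12.6 regarding diagnosis and management of adverse experiences of a potential immunologic etiology".
- Table 3 in Section 5.2.1.2, titled for non-immune events, directs the reader of events with "a potential Immune-Etiology reference Section 5.6.1.1".
- Section 7.2.3.2 introduces the guidance with "A separate guidance document has been provided entitled" and goes on to say that it covers management as well as identification and evaluation.

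**The concern.** Two parts of one protocol answer the same safety question differently. Under 12.6, a man with Grade 4 hepatitis is permanently off pembrolizumab. Under Table 5, he may restart once his steroid dose is down. These events are severe or life-threatening, and safety of the combination is part of the primary objective (Section 3.1).

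The question can come back. Table 2 gives four doses per course, and Section 7.1.5.4 sets no limit on the number of retreatment courses. The retreatment criteria in Section 7.1.5.2 are written in terms of disease status and do not mention an earlier stop for toxicity.

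**Working it through.** The check is a comparison of texts and a count; no power or sample-size figure is involved.

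**Step 1: set aside events with their own rule in the protocol body.** Section 12.6 has 11 event categories (3.1 to 3.11), so 11 x 2 = 22 combinations at Grades 3 and 4. Pneumonitis (Table 6), enterocolitis (Section 5.6.1) and infusion reactions (Table 4) have specific body rules: 3 x 2 = 6 combinations. Grade 3 colitis differs in the opposite direction, because 5.6.1 stops drug above Grade 2 while 12.6 holds it at Grade 3. There the specific body rule prevails under the 12.6 deference clause. That leaves 8 x 2 = 16.

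**Step 2: compare the remaining eight categories with Table 5** (withhold; stop only on failed steroid reduction).

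| 12.6 category | Grade 3 in 12.6 | Grade 4 in 12.6 | Differs from Table 5 on permanence |
|---|---|---|---|
| Hepatic (3.5) | stop | stop | 3 and 4 |
| Neurologic (3.6) | stop | stop | 3 and 4 |
| Renal (3.8) | stop | stop | 3 and 4 |
| Hematologic (3.4) | hold, consider stopping | stop | 4 |
| Ocular (3.7) | hold, consider stopping | stop | 4 |
| Skin (3.9) | hold | stop | 4 |
| Other immune (3.10) | hold | stop | 4 |
| Endocrine (3.3) | hold, or continue in hypothyroidism | stop for hyperthyroidism; otherwise hold or continue | 4, hyperthyroidism only |

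Differences: 3 at Grade 3 + 8 at Grade 4 = 11. Agreement on permanence: 16 - 11 = 5, all at Grade 3. Check: 6 + 5 + 11 = 22.

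Two of the 11 are weaker. Grade 3 hepatic is blurred within 12.6, where the instruction to stop is followed by a 12-week steroid-reduction condition. The endocrine entry rests on hyperthyroidism alone. Without those two, 11 - 2 = 9 differ plainly for the whole category.

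**Step 3: which text governs?**

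- *Towards 12.6:* Table 5 is a general table for events not covered elsewhere; 12.6 is a numbered section of the protocol; 5.6.1 cites it for management; and it claims to direct holding and stopping for each immune event.
- *Towards Table 5:* 12.6 defers to the protocol on dose modification and calls itself guidelines. Section 5.8 sends unacceptable toxicity to 5.2.1.2, and Table 3 there sends immune events to 5.6.1.1, which contains Table 5. Section 5.6.1.1 describes the guidance as being about identifying and evaluating irAEs.

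**Step 4: what one affected man stands to gain or lose.** An event after dose 1, 2, 3 or 4 leaves 4 - 1 = 3, 2, 1 or 0 first-course doses, plus 4 per retreatment course. A permanent stop leaves 0.

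**Step 5: how many men.** The documents give no rate. Assuming that 1% to 5% of 58 men have such an event: 58 x 0.01 = 0.58 and 58 x 0.05 = 2.9, or about 0.6 to 2.9 men.

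**The case against.** The strongest reply is that precedence is already settled. Table 5 excludes events detailed elsewhere, 12.6 details them, and a general fallback table is hardly the specific protocol language to which 12.6 defers. It is true that section 3.10 of 12.6 takes in every further Grade 3 or higher immune event and so leaves the Table 5 Grade 3-4 row with little to cover. But that may be mere redundancy, since the 3.10 rule at Grade 3 is essentially the Table 5 rule. Most of this stands, and it makes 12.6 the better reading. It does not remove the route from 5.8 through Table 3 to Table 5, and no sentence ranks the two texts.

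There are also safeguards. Irrespective of which text governs, 5.6.1.1 requires Sponsor discussion of irAEs from Grade 2 upwards. Section 5.8 removes men for unacceptable toxicity or by investigator decision. Sections 7.1.3.1 and 7.2.3.2 require acceptable laboratory results and an assessment for events of clinical interest before each dose. Table 9 requires advance approval of re-challenge after a serious, possibly drug-caused event. These limit the harm but do not supply the rule: the Table 9 approval refers back to the protocol's dose-modification guidelines, and the recurrence rule in 5.2.1.2 acts only after re-exposure.

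A reader might infer that Table 5 never stops drug, or that retreatment depends on disease status alone. Neither is right. Table 5 stops drug when the steroid dose cannot be brought down, and the checks just listed apply before every dose.

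**Conclusion.** The concern holds as an inconsistency worth correcting by amendment. Table 5 and 12.6 differ on permanence in 11 of 22 combinations, 9 of them without qualification. The textual difference is certain. How a given site would resolve it is a matter of judgment, with the balance favouring 12.6.

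A reader might go further and conclude that precedence is wholly open, or that Table 5 overrides 12.6. The documents do not support that, because Table 5 limits itself to events not detailed elsewhere. Nor do they support any effect on the PSA response test, its power or the sample size. The range of 0.6 to 2.9 men rests entirely on the assumed 1% to 5% rate.

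**What to change.** 1. Add to 5.6.1.1: *For any immune-related event listed in Section 12.6, Section 12.6 governs holding or permanently stopping pembrolizumab at every grade, except enterocolitis (Section 5.6.1), infusion reactions (Table 4) and pneumonitis (Table 6); Table 5 applies only to events not covered there.*
2. Split the Table 5 Grade 3-4 row, so that a site reading the table alone gets the same answer.
   - Grade 4: *permanently discontinue (endocrine events: follow 12.6 section 3.3).*
   - Grade 3: *withhold; permanently discontinue if prednisone equivalent cannot be reduced to 10 mg/day or less within 12 weeks; permanently discontinue at once for hepatic (AST/ALT >5 x ULN and/or bilirubin >3 x ULN), neurologic and renal events (endocrine events: follow 12.6 section 3.3).* This also settles the Grade 3 hepatic ambiguity and aligns the steroid threshold, which is below 10 mg in Table 5 and 10 mg or less in 12.6.
3. In the Grade 2 row, replace the optional hold with: *Follow Section 12.6; otherwise may withhold.* Section 12.6 requires holds for Grade 2 hepatic and renal events. It stops drug for some Grade 2 hepatic events in men with liver metastases and for ocular events that persist despite topical treatment. A precedence sentence limited to Grades 3-4 would imply that the optional hold overrides these.
4. As a clarification, add to 7.1.5.2 that men permanently discontinued from pembrolizumab for toxicity are not eligible for retreatment.

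A blanket sentence that the stricter instruction applies should be avoided: it would withhold drug in hypothyroidism, where 12.6 allows dosing to continue.

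The cost is edits to two table rows and two added sentences, in one amendment, with no extra patients, visits or procedures. The downside is that a few men whose event has resolved lose the option to restart.
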